6.14.2 Laboratory Data

Laboratory data consists of results of following examinations: serum chemistry, hematology and urine pregnancy test.

Serum chemistry will include the following variables:

- Sodium
- Potassium
- Chloride
- Bicarbonate
- Calcium
- Inorganic Phosphate
- Magnesium
- Glucose
- Amylase
- Lipase
- Lactate Dehydrogenase

QMD Ref: Worldwide-TMP-ST-005-7.0 Effective: 12Aug2019	Governing QMD: Worldwide-SOP-ST-001
Confidentiality Statement	

This document is the property of Worldwide Clinical Trials Inc. and may not be duplicated, copied, altered or removed from company without prior approval from Worldwide Quality Assurance or in compliance with Worldwide Standard Operating Procedures.

Worldwide Clinical Trials Controlled Quality Management Document			
 WORLDWIDE CLINICAL TRIALS	Sponsor:	Helixmith Co., Ltd.	
	Protocol Number:	VMALS-002-2b	
STATISTICAL ANALYSIS PLAN. PHASE 2-3-4			

- Blood Urea Nitrogen (BUN)
- Creatine Kinase (CK)
- Creatinine
- Aspartate Aminotransferase (AST)
- Alanine Aminotransferase (ALT)
- Alkaline Phosphatase
- Gamma-Glutamyl Transpeptidase (GGT)
- Total Bilirubin
- Total Protein
- Albumin

Hematology will include the following variables:

- White Blood Cells Count
- Hemoglobin
- Hematocrit
- Platelet Count
- Neutrophils Count

Serum chemistry and hematology analyses will be performed at Day 240 and Day 365. Measured values of serum chemistry and hematology analyses and their changes from baseline, will be presented with descriptive statistics at each visit by treatment group (Tables 14.3.4.1 and 14.3.4.3). Incidence of clinically significant values will be tabulated (Table 14.3.1.8), shift tables for abnormal values will be presented for each parameter (Tables 14.3.4.2, 14.3.4.4). Percentages for each parameter will be based on the number of participants who have at least one measurement for at baseline and at corresponding post-baseline visit.

Result of urine pregnancy test is variable with two possible values: positive / negative. The test should be performed only for women with childbearing potential at Day 365.

Results of serum chemistry, hematology and urine pregnancy tests will be listed (Listings 16.2.8.1 – 16.2.8.3).

6.14.3 Vital Signs

The following vital signs will be measured at Day 240, Day 300 and Day 365/ET visits:

QMD Ref: Worldwide-TMP-ST-005-7.0 Effective: 12Aug2019	Governing QMD: Worldwide-SOP-ST-001
Confidentiality Statement	

This document is the property of Worldwide Clinical Trials Inc. and may not be duplicated, copied, altered or removed from company without prior approval from Worldwide Quality Assurance or in compliance with Worldwide Standard Operating Procedures.

Worldwide Clinical Trials Controlled Quality Management Document			
 WORLDWIDE CLINICAL TRIALS	Sponsor:	Helixmith Co., Ltd.	
	Protocol Number:	VMALS-002-2b	
STATISTICAL ANALYSIS PLAN. PHASE 2-3-4			

- Systolic blood pressure (mmHg)
- Diastolic blood pressure (mmHg)
- Pulse rate (bpm)
- Respiration rate (breath / min)
- Body temperature (degrees Celsius)
- Body weight (kg)
- Body height (cm)
- Pulse oximetry (%)

Descriptive statistics for observed values and changes from baseline for vital signs including height, weight and BMI will be presented by treatment group and visit (Table 14.3.6.1). Also frequency table by the clinical significance will be presented for each vital sign (Table 14.3.6.2).

All results of vital signs measurements will be listed (Listing 16.2.8.4).

6.14.4 Electrocardiogram Data

Electrocardiograms will be performed at Day 240 and Day 365. Descriptive statistics for electrocardiogram results: general interpretation, abnormal findings and clinical significance will be presented by treatment groups (Tables 14.3.7.1 and 14.3.7.2).

All electrocardiogram results will be listed (Listing 16.2.8.5).

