1.1. Synopsis

Protocol Title: A 6-Month Extension Study Following Protocol VMALS-002-2 (A Phase 2a, Double-Blind, Randomized, Placebo-Controlled, Multicenter Study to Assess the Safety of Engensis in Participants with Amyotrophic Lateral Sclerosis)

Short Title: A 6-Month Extension Study to Assess the Safety of Engensis in Amyotrophic Lateral Sclerosis

Rationale:

The purpose of this study is to evaluate the long-term safety of intramuscular (IM) administration of Engensis in Participants with Amyotrophic Lateral Sclerosis (ALS) who were previously randomized, received treatment, and completed the Day 180 Visit of Study VMALS-002-2. Safety will be assessed by incidences of treatment-emergent adverse events (TEAEs), treatment-emergent serious adverse events (TESAEs), adverse events of special interest (AESIs), and the clinically significant laboratory values. See the table below for additional, exploratory endpoints.

Engensis contains the active pharmaceutical ingredient VM202, a novel genomic complementary deoxyribonucleic acid (cDNA) hybrid human hepatocyte growth factor (HGF) coding sequence (HGF-X7) expressing two isoforms of HGF, HGF₇₂₈ and HGF₇₂₃, being developed by Helixmith for treatment of ALS.

Data from Helixmith's first clinical trial in ALS, the Phase 1/2 study (VMALS-001) that included 18 Participants who were followed for 9 months, suggested that targeted delivery of HGF to motor neurons via intramuscular (IM) injections of Engensis was safe and well-tolerated. Safety assessments during the study included reports of 79 adverse events (AEs) in 17 Participants (94.4%), including 26 mild injection site reactions (Grade 1). Five SAEs were reported in 3 Participants. Only an injection site reaction was considered related to study treatment. Following injections until Day 90, a plateau or a relative slowing in the decline of the Revised Amyotrophic Lateral Sclerosis Function Rating (ALSFRS-R) scores and muscle strength was noted, suggesting a slowing of disease progression. After 90 days, the plateau was no longer observed in the ALSFRS-R, with the notable exception of a trend toward better preservation of bulbar and breathing functions as measured by the ALSFRS-R.

Data for Participants at study visits in Study VMALS-002-2 will be used as reference points for changes in safety assessments during the extension study VMALS-002-2b.

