8.1.1. Complete Physical Examinations

A complete physical examination (PE) will be performed on Days 240 and 365/ET. The complete PE will include the following: an examination of the skin/integumentary systems, general appearance, head, neck (including thyroid), eyes, ears, nose, throat, lymph nodes, chest (lungs), heart, abdomen, musculoskeletal system, neurological system, and any additional assessments needed to establish Baseline status or evaluate symptoms or TEAEs. Any abnormalities should be categorized as clinically significant (CS) or not clinically significant (NCS), and clinically significant abnormalities should be recorded as TEAEs, TESAEs, or AESIs. Investigator or qualified medical personnel who routinely perform these evaluations in patients with ALS will conduct the examination, determine findings, and assess any abnormalities as to their clinical significance.

8.1.2. 12-Lead Electrocardiograms

12-Lead ECGs will be performed on Days 240 and 365/ET. Any clinically significant abnormalities are to be recorded as TEAEs. The ECG recording will be printed out and stored with the Participant's records.

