6.2.2 Baseline

Baseline is defined as the last non-missing value (either scheduled, unscheduled or repeat) before the participant receives first Study Injection in the Study VMALS-002-2.

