6.14.1.4 Outputs planned for Adverse Events

TEAEs with start date and time before date and time of the Informed Consent for VMALS002-2B will be presented in a separate listing and will not be tabulated.

The following tables will be presented:

- Summary of TEAEs (Table 14.3.1.1)
- TEAEs by System Organ Class and Preferred Term (Table 14.3.1.2)
- TESAEs by System Organ Class and Preferred Term (Table 14.3.1.3)
- TEAEs by System Organ Class and Preferred Term and Maximum Severity (Table 14.3.1.4)

QMD Ref: Worldwide-TMP-ST-005-7.0 Effective: 12Aug2019	Governing QMD: Worldwide-SOP-ST-001
Confidentiality Statement	

This document is the property of Worldwide Clinical Trials Inc. and may not be duplicated, copied, altered or removed from company without prior approval from Worldwide Quality Assurance or in compliance with Worldwide Standard Operating Procedures.

Worldwide Clinical Trials Controlled Quality Management Document			
 WORLDWIDE CLINICAL TRIALS	Sponsor:	Helixmith Co., Ltd.	
	Protocol Number:	VMALS-002-2b	
STATISTICAL ANALYSIS PLAN. PHASE 2-3-4			

- TEAEs by System Organ Class and Preferred Term and Maximum Relationship (Table 14.3.1.5)
- TESAEs by System Organ Class and Preferred Term and Maximum Severity (Table 14.3.1.6)
- TESAEs by System Organ Class and Preferred Term and Maximum Relationship (Table 14.3.1.7)
- Incidence of Clinically Significant Laboratory Values (Table 14.3.1.8)
- AESIs by System Organ Class and Preferred Term (Table 14.3.1.9)

The following listings will be provided:

- All TEAEs (Listing 16.2.7.1)
- AESIs (Listing 16.2.7.2)
- TESAEs (Listing 16.2.7.3)
- TEAEs leading to study discontinuation (Listing 16.2.7.4)
- TEAEs related to study medication (Listing 16.2.7.5)
- TESAEs leading to death (Listing 16.2.7.6)
- AEs that registered as not TEAEs (Listing 16.2.7.7)

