6.14.5 Physical Examination

Complete physical examination will be performed at Day 240 and Day 365.

The following body systems will be examined:

- HEENT (Head, Eye, Ear, Nose, Throat)
- Heart
- Lungs
- Abdomen
- Extremities
- Lymph Nodes
- Neurological
- Musculoskeletal System
- Skin/Integumentary Systems

QMD Ref: Worldwide-TMP-ST-005-7.0 Effective: 12Aug2019	Governing QMD: Worldwide-SOP-ST-001
Confidentiality Statement	

This document is the property of Worldwide Clinical Trials Inc. and may not be duplicated, copied, altered or removed from company without prior approval from Worldwide Quality Assurance or in compliance with Worldwide Standard Operating Procedures.

Worldwide Clinical Trials Controlled Quality Management Document			
 WORLDWIDE CLINICAL TRIALS	Sponsor:	Helixmith Co., Ltd.	
Protocol Number:			VMALS-002-2b
STATISTICAL ANALYSIS PLAN. PHASE 2-3-4			

Each parameter will be presented with frequencies and percentages of values (Normal, Abnormal not Clinically Significant, Abnormal Clinically Significant) in shift tables based on baseline for each treatment group (Table 14.3.6.3). Percentages will be based on the number of participants who have measurement at baseline and at corresponding post-baseline visit.

A listing of physical examination results will be presented (Listing 16.2.8.6).

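### SAP 6.14.4 plans no baseline comparison for ECG, so its by-arm tables cannot separate old abnormalities from new ones judged not clinically significant

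*SAP*

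**What the plan says.** SAP 6.14.4 has ECGs at Day 240 and Day 365 and two tables (14.3.7.1 and 14.3.7.2), in which "general interpretation, abnormal findings and clinical significance will be presented by treatment groups". All results also go into Listing 16.2.8.5. The section mentions no baseline value, change or shift.

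The comparable sections do:

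- Laboratory data (SAP 6.14.2): changes from baseline, and "shift tables for abnormal values will be presented for each parameter".
- Vital signs (SAP 6.14.3): "Descriptive statistics for observed values and changes from baseline for vital signs".
- Physical examination (SAP 6.14.5): normal, abnormal not clinically significant and abnormal clinically significant, "in shift tables based on baseline for each treatment group".
- SVC (SAP 6.15.5): changes from baseline by visit and arm.

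The SAP's general baseline rule is available for ECG too: "Baseline is defined as the last non-missing value (either scheduled, unscheduled or repeat) before the participant receives first Study Injection" in the core study (SAP 6.2.2). The protocol synopsis (1.1) states the intent: "Data for Participants at study visits in Study VMALS-002-2 will be used as reference points for changes in safety assessments". On the recording side, Protocol 8.1.2 says of ECGs: "Any clinically significant abnormalities are to be recorded as TEAEs".

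**The concern.** A by-arm count of abnormal ECGs at Day 240 or Day 365 adds together participants who were abnormal before any injection and participants who became abnormal afterwards. Only the second group bears on the safety of Engensis. In groups this small, chance imbalance in the first group can hide a real excess in the second, or look like an excess when there is none.

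Much of the ECG information is protected by other routes. What is left is an ECG that is new or worse than baseline but judged not clinically significant. It does not become a TEAE on that ground, so Tables 14.3.7.1 and 14.3.7.2 are its only tabulation. Cardiac findings matter for this product: Protocol 2.3.1 names plaque instability from angiogenesis as a risk, and reports a myocardial infarction that the sponsor categorised as possibly related.

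**Working it through.** **Text check.** The general rules do not fill the gap. SAP 6.2.2 defines baseline, 6.2.13 says which post-baseline values are tabulated, and 6.3 sets summary formats. None adds an ECG comparison. SAP 9 reports no departure from the protocol's planned analysis, so the omission is not explained there.

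**What other outputs already cover:**

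| ECG situation | Where it is tabulated | New separated from old? |
|---|---|---|
| Clinically significant, new or worse | TEAE tables | Yes, by the TEAE definition |
| Coronary diagnosis since baseline | "AESIs by System Organ Class and Preferred Term (Table 14.3.1.9" in SAP 6.14.1.4) | Yes |
| Abnormal heart examination | Table 14.3.6.3 | Yes, shift from baseline |
| New or worse, not clinically significant | Tables 14.3.7.1 and 14.3.7.2 only | No |

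**Logic.** If a by-arm table shows *m* participants with an abnormal but not clinically significant ECG, the number who are new can be anything from 0 to *m*. A separate baseline count would not in general settle it. Only a within-participant cross-tabulation does.

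**Illustration of size.** The plan gives no figure to reproduce.

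Inputs:
- Total of at most 18 participants (SAP 4).
- Arm split 9:9 or 12:6 (assumed; not in these documents).
- Prevalence *p* of an abnormal ECG at baseline of 10%, 30% or 50%, the same in both arms (assumed).
- Baseline abnormalities persist (assumed).

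Let X1 ~ Bin(n1, *p*) be the number abnormal at baseline on Engensis and X2 ~ Bin(n2, *p*) the number on placebo, independent. Probabilities are exact sums.

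*Case 1, masking.* *k* Engensis participants become newly abnormal and no placebo participant does. The by-arm table shows Engensis equal or lower with probability P((X1 + k)/n1 ≤ X2/n2 | n1 − X1 ≥ k):

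| Split, new cases | *p* = 10% | *p* = 30% | *p* = 50% |
|---|---|---|---|
| 9:9, k = 2 | 11% | 22% | 25% |
| 12:6, k = 2 | 20% | 29% | 31% |
| 9:9, k = 3 | 2% | 10% | 13% |
| 12:6, k = 3 | 8% | 18% | 21% |

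Counting only a strictly lower Engensis percentage, k = 2 gives 2%, 10% and 12% at 9:9, and 8%, 18% and 21% at 12:6.

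*Case 2, spurious difference.* Nobody becomes newly abnormal. The arms differ by 20 points or more with probability P(|X1/n1 − X2/n2| ≥ 0.20):

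| Split | *p* = 10% | *p* = 30% | *p* = 50% |
|---|---|---|---|
| 9:9 | 22% | 44% | 48% |
| 12:6 | 14% | 37% | 41% |

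At 9:9 one participant is 1/9 = 11 points, so 20 points means a difference of at least two participants.

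A shift table would show 2 versus 0 (or 3 versus 0) new cases in case 1, and 0 versus 0 in case 2.

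**The case against.** The strongest reply is that little of importance is left uncovered. Clinically significant ECG changes are TEAEs, and the TEAE definition already refers to results that worsen from baseline, so the investigator makes the comparison. ECG is not itself a primary endpoint, nothing is tested (Protocol 9.3.1), and a reader can go through 18 participants in a listing sorted by arm and participant. That limits the weight of the point, but does not remove it. The investigator's comparison yields no table for findings below the clinical-significance threshold. The listing helps only if it includes core-study ECGs, which SAP 6.14.4 does not say. Physical examination has the same small numbers and a listing, yet gets a shift table.

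Two replies concern what cannot be seen. The titles and shells of the two ECG tables are not readable in the public SAP, so a shift layout might exist there. These documents also do not show that the core study recorded a pre-injection ECG. Both stand as caveats. The first means the point rests on the SAP text, which names shift tables where it plans them. The second decides which form the fix takes.

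It is also fair that the synopsis sentence prescribes no particular table, and that the SAP gives only a frequency table for the clinical significance of vital signs (Table 14.3.6.2). Vital signs, however, also get changes from baseline in Table 14.3.6.1, and ECG gets nothing equivalent.

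Finally, the illustration reduces ECG to abnormal or not, whereas a distinctive new finding might show in the abnormal-findings rows. It also counts ties as masking, which is why the strict figures are given as well.

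**Conclusion.** The point holds, and it is minor. As described in SAP 6.14.4, ECG is a safety assessment without the baseline reference that the SAP applies to laboratory data, vital signs, physical examination and SVC. The consequence is confined to ECG changes not judged clinically significant, and to how descriptive tables read; no decision rule depends on it. With two new Engensis cases the masking probability is 11% to 31%, and the probability of a spurious gap of 20 points or more is 14% to 48%. Both ranges rest on the assumed prevalences and arm splits; masking also rests on the assumed number of new cases and on persistence of baseline abnormalities.

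**What to change.** Keep the planned ECG summary. Add to SAP 6.14.4 a shift table (normal, abnormal not clinically significant, abnormal clinically significant) from the VMALS-002-2 pre-injection baseline of SAP 6.2.2 to Day 240 and to Day 365/ET, by treatment received, in the layout of Table 14.3.6.3. Include one row counting participants whose ECG is new or worse than baseline. If the core study has no pre-injection ECG, say so in 6.14.4 as the reason no baseline comparison is made.

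The cost is one sentence and one table in a format already planned, with no new procedures. The small downside is that participants without a baseline ECG drop out of the shift table; they remain in the planned summary and the listing.

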6.14.5 Physical Examination

Complete physical examination will be performed at Day 240 and Day 365.

The following body systems will be examined:

- HEENT (Head, Eye, Ear, Nose, Throat)
- Heart
- Lungs
- Abdomen
- Extremities
- Lymph Nodes
- Neurological
- Musculoskeletal System
- Skin/Integumentary Systems

QMD Ref: Worldwide-TMP-ST-005-7.0 Effective: 12Aug2019	Governing QMD: Worldwide-SOP-ST-001
Confidentiality Statement	

This document is the property of Worldwide Clinical Trials Inc. and may not be duplicated, copied, altered or removed from company without prior approval from Worldwide Quality Assurance or in compliance with Worldwide Standard Operating Procedures.

Worldwide Clinical Trials Controlled Quality Management Document			
 WORLDWIDE CLINICAL TRIALS	Sponsor:	Helixmith Co., Ltd.	
Protocol Number:			VMALS-002-2b
STATISTICAL ANALYSIS PLAN. PHASE 2-3-4			

Each parameter will be presented with frequencies and percentages of values (Normal, Abnormal not Clinically Significant, Abnormal Clinically Significant) in shift tables based on baseline for each treatment group (Table 14.3.6.3). Percentages will be based on the number of participants who have measurement at baseline and at corresponding post-baseline visit.

A listing of physical examination results will be presented (Listing 16.2.8.6).

6.15 Exploratory Analyses

6.15.1 Revised Amyotrophic Lateral Sclerosis Functional Rating Scale (ALSFRS-R)

ALSFRS-R will be measured at Day 240, Day 300 and Day 365. Total score and subscores for Fine and Gross Motor Functions (sum of scores for items 4 to 9) and for Bulbar Function (sum of scores for items 1 to 3) their changes from baseline will be presented with descriptive statistics by visits and treatment group (Table 14.6.1, Listing 16.2.9.1).

Slope of the total score will be provided using graphical presentation of values by visit for both treatment group. The figures will be presented using time points from both VMALS-002-2 and VMALS-002-2b studies.

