9. STATISTICAL CONSIDERATIONS

Detailed statistical methods are described in the Statistical Analysis Plan (SAP).

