3.2 Exploratory Endpoints

- Change from Baseline (Study VMALS-002-2 Day 0) in total mean Revised Amyotrophic Lateral Sclerosis Function Rating (ALSFRS-R) scores at Day 365 for Engensis compared to Placebo
- Change from Baseline (Study VMALS-002-2 Day 0) in ALSFRS-R subscores for Fine and Gross Motor Functions (sum of scores for items 4 to 9) and for Bulbar Function (sum of scores for items 1 to 3) at Day 365 for Engensis compared to Placebo
- Changes in the slope of the total ALSFRS-R score over time for Engensis compared to Placebo
- Change from Baseline (Study VMALS-002-2 Day 0) in muscle strength assessed bilaterally by Handheld Dynamometry (HHD) in muscles in the upper and lower extremities at Day 365 for Engensis compared to Placebo
- Change from Baseline (Study VMALS-002-2 Day 0) in Quality of Life (QoL) using the ALS Assessment Questionnaire (ALSAQ; with 40 items, ALSAQ 40) on Day 365 for Engensis compared to Placebo
- Patient Global Impression of Change (PGIC) and Clinical Global Impression of Change (CGIC) at Day 365 for Engensis compared to Placebo
- Change from Baseline (Study VMALS-002-2 Day 0) in Slow Vital Capacity (SVC) at Day 365 for Engensis compared to Placebo
- Time to tracheostomy for Engensis
- Time to all-cause mortality compared to Placebo

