6.2.9 Revised Amyotrophic Lateral Sclerosis Functional Rating Scale (ALSFRS-R)

Subscore for Fine and Gross Motor Functions will be calculated as sum of scores for items 4 to 9; subscore for Bulbar Function will be calculated as sum of scores for items 1 to 3. Total score will be calculated as sum of scores for items 1 to 9.

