6.3 Conventions

All data listings, summaries, figures and statistical analyses will be generated using SAS version 9.4 or higher¹ unless otherwise noted.

Summaries will be presented by treatment group. Treatment group labels will be displayed as follows:

Engensis (N=XX)	Placebo (N=XX)	Overall (N=XX)
--------------------	-------------------	-------------------

Listings will be sorted in the following order treatment group, Participant, parameter unless otherwise stated. All data will be listed.

Continuous variables will be summarized by the number of non-missing observations, mean, median, standard deviation, and minimum and maximum. For all tabulations of changes from baseline data, the lower and upper 95% confidence limits for the mean for the individual treatments will be given.

Categorical variables will be summarized by presenting the frequency and percent. Percentages will be based on the number of non-missing observations or the participant population unless otherwise specified. For each variable, all categories will be shown. Zero frequencies (but not the percent) within a category will be presented.

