9 CHANGES TO PLANNED PROTOCOL ANALYSIS

There are no changes to the planned protocol analysis.

QMD Ref: Worldwide-TMP-ST-005-7.0 Effective: 12Aug2019	Governing QMD: Worldwide-SOP-ST-001
Confidentiality Statement	

This document is the property of Worldwide Clinical Trials Inc. and may not be duplicated, copied, altered or removed from company without prior approval from Worldwide Quality Assurance or in compliance with Worldwide Standard Operating Procedures.

Worldwide Clinical Trials Controlled Quality Management Document			
 WORLDWIDE CLINICAL TRIALS	Sponsor:	Helixmith Co., Ltd.	
	Protocol Number:	VMALS-002-2b	
STATISTICAL ANALYSIS PLAN. PHASE 2-3-4			

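### The exploratory ALSFRS-R slope endpoint is a comparison with placebo, but the visible SAP text plans only a graph of values by visit and specifies no slope estimate, between-arm difference or interval

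*SAP*

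**What the plan says.** SAP 3.2 lists the endpoint as "Changes in the slope of the total ALSFRS-R score over time for Engensis compared to Placebo", and protocol sections 1.1 and 3 carry the same wording. SAP 6.15.1 gives the method: "Slope of the total score will be provided using graphical presentation of values by visit for both treatment group". It adds: "The figures will be presented using time points from both VMALS-002-2 and VMALS-002-2b studies".

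The tabulated ALSFRS-R output in the same section covers the total and subscores, and "their changes from baseline will be presented with descriptive statistics by visits and treatment group (Table 14.6.1, Listing 16.2.9.1"). SAP 6.3 adds an interval to every change-from-baseline table: "the lower and upper 95% confidence limits for the mean for the individual treatments will be given". SAP 6.2.9 derives two subscores and a total, and no slope. Its definition of the total is: "Total score will be calculated as sum of scores for items 1 to 9". Protocol section 9 leaves methods to the SAP: "Detailed statistical methods are described in the Statistical Analysis Plan (SAP").

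**The concern.** A slope is a rate of change, and the endpoint asks for a comparison of rates between arms. A graph of scores by visit provides neither as a number. Followed as written, the plan would leave readers to judge the slopes and their difference by eye, in at most 18 people, with nothing to show how uncertain the comparison is.

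The risk of over-reading is concrete. The protocol synopsis already describes the earlier open-label ALS study in terms of a plateau or slower decline. The extension has a randomised placebo group to set beside Engensis, but that advantage is largely lost if the slope comparison is only visual.

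**Working it through.** **Step 1. Does any planned output give a slope or a slope difference?**

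| Place | What it provides | Slope per arm? | Between-arm slope difference? |
|---|---|---|---|
| SAP 6.2.9 | Two subscores and a total | No | No |
| SAP 6.15.1, table | Scores and changes from baseline by visit and arm | No | No |
| SAP 6.3 | 95% limits for each arm's mean change | No | No |
| SAP 6.15.1, figure | Values by visit, both arms | Visual only | Visual only |
| Protocol 9.3 | Primary safety endpoints only | No | No |

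No regression, mixed model or per-participant slope appears in the visible text.

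**Step 2. Are there enough data to estimate one?**

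SAP 6.2.3 takes tracheostomy from ALSFRS-R item 12. SAP 6.15.6 lists the visits used for that analysis: after screening, Days 0, 30, 60, 84, 120, 144, 180, 240, 300 and 365. It is therefore reasonable to infer up to 10 scores per participant from Day 0.

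**Step 3. How precise would the estimate be?**

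The plan has no figure to reproduce: the documents give no slope SD, residual SD, effect size or allocation ratio. What follows is an illustration.

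- From the documents: the visit days above; at most 18 participants (SAP section 4).
- Assumed: 9 per arm, every visit complete, between-participant slope SD 0.4 to 0.8 points per month, residual SD 1.5 to 2.5 points.

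Spread of visit times: the mean day is 1523/10 = 152.3 and the sum of squared deviations is 127,964 days². Dividing by 30.4375² (the SAP's days per month) gives Sxx = 138 months².

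Standard error of the slope difference, n per arm:

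SE = sqrt(2 × (SD_slope² + SD_res²/Sxx) / n)

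- Low end: sqrt(2 × (0.16 + 2.25/138)/9) = sqrt(2 × 0.1763/9) = 0.198
- High end: sqrt(2 × (0.64 + 6.25/138)/9) = sqrt(2 × 0.6853/9) = 0.390

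The 95% half-width is t(16) = 2.12 times the SE:

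- 2.12 × 0.198 = 0.42 points per month
- 2.12 × 0.390 = 0.83 points per month

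With 5 per arm and the same SDs, t(8) = 2.306 and the SEs are 0.266 and 0.524, so the half-width is 0.61 to 1.21. Missed visits would widen these further.

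The slope SD dominates: the residual part adds only 0.016 to 0.045 to a variance of 0.16 to 0.64. Simple per-participant slopes would therefore lose little against a mixed model when follow-up is complete.

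**The case against.** The strongest case against is proportion. The endpoint is exploratory, the study is a safety extension of at most 18 people, SAP 6.11 marks efficacy analyses as not applicable, and most other exploratory outcomes are only summarised. A graph could be a deliberate choice. This limits the weight of the point, and rewording the endpoint as a descriptive plot would also remove the mismatch. It does not remove the mismatch as the documents stand. A slope difference with an interval is itself descriptive, and the SAP specifies Kaplan-Meier analysis for other exploratory endpoints.

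A reader might also infer four stronger things that the documents do not support:

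- *That SAP section 9 is contradicted.* It says "There are no changes to the planned protocol analysis". The protocol sets out no slope method, so there was none to depart from.
- *That everyone who leaves early is lost from the Day 365 change.* SAP 6.2.13 combines Early Termination data with Day 365, and protocol 7.1 includes the ALSFRS-R at that visit where possible. Only people without such an assessment drop out, including those who die without one.
- *That the figure must show survivors only.* SAP 6.15.1 does not say whether it plots means or individual lines. Late means would come from those still attending, but individual lines would show the earlier course of those who left.
- *That no slope will ever be estimated.* The SAP's list of outputs is blacked out, and SAP section 6 allows added analyses in the study report. The claim is limited to what the visible text specifies in advance.

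**Conclusion.** The point holds for the visible SAP text. The slope endpoint is worded as a comparison with placebo, and its only planned analysis is a graph, so no slope per arm, slope difference or interval would be reported. The gap is worth closing because an estimate is feasible and cheap, but it does not affect the primary safety conclusions.

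The estimate would be imprecise: about ±0.42 to ±0.83 points per month at best, under the assumed SDs, 9 per arm and complete visits, for one overall slope. That imprecision is a reason to print the interval, because a plot without one can make a chance separation look like an effect.

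Two matters must be settled first. SAP 6.2.9 sums items 1 to 9, whereas protocol 8.2.1 describes twelve items scored 0 to 48, so the modelled outcome is unclear. The endpoint also does not say whether a change in slope means a difference between arms or a change within an arm over time.

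**What to change.** In SAP 6.2.9 and 6.15.1:

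1. Reconcile the ALSFRS-R total with protocol 8.2.1.
2. State which meaning of a change in slope is intended. A knot at Day 180 is at most an optional secondary analysis: it marks the boundary between the studies, and the documents give no other reason for it.
3. Model all scheduled totals from both studies, including Early Termination scores, on actual days from first injection, so that an early score is not placed at Day 365. Use a random intercept and slope with arm, time and arm-by-time. If the model does not converge, use per-participant least-squares slopes.
4. Report each arm's slope and the Engensis-minus-placebo difference with a 95% confidence interval, without a formal test. Keep the figure as support.
5. State as a limitation that the analysis set holds only people who completed Day 180 (protocol section 5) and consented to the extension (SAP 6.1.1). Neither method removes that selection.

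The cost is SAP wording and one program, with no new data collection. The drawback is a wide interval. If the sponsor wants only the figure, the endpoint should be reworded as a descriptive plot.
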